Objectives

Primary research question

Based on the description provided and existing evidence, we posed the following research question: *Is the use of Zoles customised 3D-printed insoles, for a duration of 8 weeks, superior to a "do-as-usual" control strategy in improving running-related pain among frequent recreational runners participating in regular parkrun activities?*

This research question was designed using the PICOT model with the following specifications for each element [35]:

Population: Frequent recreational runners participating in regular parkrun activities.

Intervention: Zoles customised 3D-printed TPU insoles for ~8 weeks.

Control: "Do-as-usual" control group.

Outcome: Improvement in running-related pain.

Time frame: 10 weeks after baseline (~8 weeks after receiving allocated intervention).

Primary objective

The primary objective is to determine the effectiveness of the Zoles customised 3D-printed insoles on the change in running-related pain 10 weeks after baseline in frequent recreational runners participating in regular parkrun activities.

Primary research hypothesis

Our hypothesis is that the Zoles customised 3D-printed insoles, will lead to a significant reduction in running-related pain 10 weeks after baseline (~8 weeks after received allocated intervention) compared to a "do-as-usual" control strategy among frequent recreational runners participating in regular parkrun activities.

Secondary objectives

1. To assess the effect of Zoles customised 3D-printed insoles on secondary outcomes like:
 - a. Global Rating of Change (GRoC) in overall daily pain and discomfort [36].
 - b. Running-related foot/footwear comfort [37].
 - c. 5-k (parkrun) completion time.
 - d. Running-related injury incidence rate.
 - e. Time-loss from running.
 - f. Running exposure in terms of miles and time.
 - g. Adherence to the intervention during daily- and running activities.
 - h. Adverse events from using the Zoles insoles.
2. To explore if the control group benefits similarly to receiving customised 3D-printed insoles when provided after the initial 10-week primary trial phase.
3. To understand the long-term effects and durability of the benefits of the Zoles customised 3D-printed insoles, assessed one year after the intervention.
4. To investigate the immediate therapeutic effect of Zoles insoles specifically for participants with clinically relevant baseline pain levels (11-NRS ≥ 3) [38].

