The allocation phase (Timepoint 0) commences post-enrolment, where participants are sent a baseline questionnaire. The information gathered from this questionnaire is used in the balanced block randomisation procedure. Upon completion of the baseline questionnaire, participants are set up to receive weekly follow-up surveys during the primary study period (Weeks 1-10). During this period, there is weekly follow-up on primary and secondary outcomes, delivery of allocated intervention group insoles projected before week 3, and weekly monitoring of adherence and adverse effects. In a case where a pair of insoles do not fit inside a participant's footwear, a fast-track adjustment, production, and shipment procedure takes place, ensuring a minimal delay of insole delivery of approximately one week.

In the control group step allocation period (Weeks 10-18), control group participants receive their customised insoles and all participants are sent a single event follow-up questionnaire at week 18. This questionnaire covers primary and secondary outcomes, as well as adherence and adverse effects.

Finally, post-market surveillance occurs at Timepoint Week 52, a year after the study's commencement. All participants receive a follow-up questionnaire assessing their post-trial experiences with the insoles, any adverse effects experienced during the year, and the long-term effects of the Zoles insoles (Figure 3).

Sample size

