The trial will include prospective data collection using e-mail-distributed surveys via REDCap (Vanderbilt University, Nashville, TN, USA). Participants receive these surveys weekly for the initial 10 weeks, facilitating the collection of real-time data on their experience, pain levels, and the impact of the customised insoles for those in the intervention group. At the conclusion of this primary trial period (week 10), participants in the control group are provided with their customized insoles, marking the commencement of an additional 8-week observation period to compare intervention response between both groups (week 18). The final follow-up occurs at the 52-week mark, again via REDCap to provide insights on their long-term experiences, adverse effects, and the sustained impact of the Zoles insoles on their running-related pain and comfort.

Reminders will automatically be sent to participants at 24 hours and 48 hours after the original time of a follow-up questionnaire to participants failing to respond. Investigators will contact participants via telephone and SMS after another 24 hours if still not responding after receiving reminders to reduce the amount of missing data.

Data management

Every participant is assigned a unique identification number, ensuring their anonymity throughout the study in compliance with the General Data Protection Regulations (GDPR) under the Data Protection Act 2018.

Data collection, both at baseline and throughout the prospective stages, is facilitated via REDCap, a secure and robust online platform renowned for its data management capabilities [56]. This process is overseen from Department of Clinical Medicine at Aalborg University (DK-9220, Aalborg Øst, Denmark) by a dedicated data handler (CD), who remains blinded to group allocation. CD and FGL constitute the Data Monitoring Committee. A list of responding and non-responding participants is generated weekly, wherefrom a list of non-responding participants to contact is generated.

The Study Director (FGL) will maintain a secured key to the participants' identities, stored on a two-factor secured personal drive, ensuring the capability to identify and withdraw individual data if necessary.

All data is safeguarded within GDPR compliant two-factor and password-protected systems at St. Mary's University server, and on the REDCap online system. These measures ensure that the data remains inaccessible to unauthorized personnel, preserving confidentiality.

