In adherence to transparency and scientific scrutiny, a fully anonymised dataset at the participant level, accompanied by the corresponding statistical code, will be made available to the public, contingent upon the requirements of the journal publishing the study's findings. This disclosure ensures the replicability and verification of the research while upholding the anonymity and privacy of all participants.

The published results will omit any information that could potentially be used to identify individual participants.

Statistical methods

The primary outcome; change in running-related pain from baseline to follow-up, will be calculated using negative binomial regression. Figure 4 illustrates a hypothetical change in pain over the course of the trial, including the expected catch-up by the control group at week 18. It is important to note, however, that the between-groups analysis for difference will adjust for

values reported at baseline [49,57]. Both the Global Rating of Change (GROC) in overall daily pain and discomfort and running-related foot/footwear comfort will be calculated similarly. Injury incidence rate ratios will be estimated per 1000 hours of running exposure using Poisson regression. Mean time-loss from running will be calculated using negative binomial regression. Adherence to the intervention will be descriptively analysed and presented, and adverse event due to the Zoles insoles will be presented in type and frequency. Every analysis in the main trial report will abide by the intention to treat principle, which means including all participants in the analyses, regardless of intervention adherence-signifying that participants will be analysed based on initial randomisation. In the primary trial report, all collected outcomes will be listed, and it will also be stated that the below-mentioned 'other pre-specified outcomes' will be reported in a subsequent secondary analysis publication with a clear reference to the primary trial registration.

Possible effect modifiers include time with allocated intervention due to possible logistics issues in handing over the insoles to the intervention group, as well as any last-minute needs for sizing adjustments if a pair of insoles do not fit inside a participant's footwear. Any new injury sustained during the trial period is another potential effect modifier. No potential external effect modifiers will be factored in the intention-to-treat analyses.

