Despite these challenges, the study's structure and methodology have been meticulously crafted to yield insights that are both scientifically rigorous and practically insightful, balancing between the ideal conditions for experimental control and the complexities of real-world application. Conversely, this study boasts several strengths that bolster its reliability and validity. The use of blinded group allocation sequence, external outcome assessors who are blinded to the group assignments, and an external data manager also blinded to group allocation ensures objectivity in data collection and analysis, minimizing bias. Furthermore, the recording of all outcomes in participants' natural environments, including baseline data, amplifies the real-world applicability of the findings. Participants are thus not influenced by the study personnel, ensuring the outcomes reflect the real-life effect of the intervention, enhancing the study's external validity. Additionally, the employment of a mobile scanning unit allows us to recruit participants from more distant parkrun locations, thus allowing for enrolment of participants who might not have the means to travel across London to partake in this study.

The intention to treat analysis in the primary study report ensures all participants are included in the final analysis, maintaining the randomisation benefits and offering a conservative estimate of the intervention's effectiveness. The step-wedge design addition enhances the study's robustness, allowing immediate verification of effectiveness by comparing the control group's response post-primary trial period to the intervention. The inclusion of a 52-week post-market surveillance further elevates the study's comprehensiveness, offering insights into the long-term effects and usability of the insoles.

Transparency is maintained through pre-registration of the study and the detailed description of the intervention using the TIDieR checklist [45], ensuring replicability and openness in reporting. The publication of this study protocol underscores the commitment to transparent and ethical research practices, contributing to the broader scientific discourse and public scrutiny.

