Zoles ApS and affiliates have no role in the study, and are restricted from any involvement in the design of the study, execution, analyses, interpretation of data, writing of the manuscript, or in the decision to submit for publication. The Study Director has full authority of the trial administration and decision for publication.

Funding

This is an investigator-initiated trial. The funding for this study is provided by St Mary's University Faculty of Sport, Technology and Health Sciences (STHS) QR Funds. Zoles ApS has graciously contributed the customised 3D printed insoles for all study participants, valued at approximately £23,000. Zoles ApS is also responsible for supplying the 3D scanners

(DOMEscan/IBV, Instituto de Biomecanica de Valencia, 46022, Valencia, Spain) that are used to scan the participants' feet, training and support of St Mary's staff members.

Authors' contributions

FGL is the study director, he conceived the study, led the proposal and protocol development, primary supervisor overseeing the overall conduct of the study. SI is the principal investigator, leading the core investigative efforts. RM and CD shared the role of study chair; RM also acted as co-supervisor, while CD managed data collection. KT, also a study chair, contributed senior clinical trial expertise and senior supervision. All authors participated in designing the study, refining the protocol, and approved the final study registration and manuscript.

Acknowledgements

We express our thanks to the local parkrun organisers for their support and collaboration. Their assistance in participant recruitment will be crucial to this study's initiation and progress.

Figures

Figure 1: Zoles 3D-printed insole exemplar. Picture provided and used with permission from Zoles ApS.

Figure 2: Example of foot scanning process of a right foot using the DOMEscan/IBV 3D scanner.

Figure 3: Participant timeline in the SPIRIT (Standard protocol items: Recommendations for interventional trials) diagram

Figure 4: Visualisation of change in pain score in the intervention (blue) and control group (red), respectively (Example, not based on data).

Figure 1

[figure not shown]
Figure 2

Figure 3

| | STUDY PERIOD | | | | | | | | | | | Control group step allocation | Post-market surveillance | |
|---------------------------------------|--------------|------------|----------------------|---|---|---|---|---|---|---|---|-------------------------------|--------------------------|----|

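### No untreated arm remains after week 10, so the step to insoles cannot by itself verify effectiveness at week 18 or show durability at week 52, and neither analysis is specified

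*Combined protocol and SAP*

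**What the plan says.** **Supply.** Figure 3 shows the control condition ending at week 10. Procedures and data collection says controls receive their insoles at the end of the primary period, "marking the commencement of an additional 8-week observation period to compare intervention response between both groups (week 18"). Participant timeline says that in this period "control group participants receive their customised insoles and all participants are sent a single event follow-up questionnaire at week 18". For the intervention arm it gives "delivery of allocated intervention group insoles projected before week 3", and the PICOT time frame is "10 weeks after baseline (~8 weeks after receiving allocated intervention").

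**Week 18.** Secondary objective 2 is "To explore if the control group benefits similarly to receiving customised 3D-printed insoles when provided after the initial 10-week primary trial phase". Statistical methods describes a hypothetical course of pain, "including the expected catch-up by the control group at week 18". The Figure 4 legend marks that curve as illustrative: "respectively (Example, not based on data").

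**Week 52.** Secondary objective 3, and the section on secondary subgroup analysis and post-market surveillance, aim at long-term effects and durability of benefit. Neither names a comparator.

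**What is specified.** Primary outcome and Statistical methods define one pain contrast in full: between-group change from baseline to week 10, adjusted for baseline, by negative binomial regression. The statement that an analysis will follow the primary outcome's method refers to participants with clinically relevant baseline pain, not to week 18 or week 52.

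**What is claimed.** Strengths and limitations says the step enhances robustness, "allowing immediate verification of effectiveness by comparing the control" group's response after the primary period with the intervention.

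**The concern.** Verifying effectiveness needs a contrast that behaves differently when the insoles work and when they do not. After week 10 both arms have been supplied, and the plan does not say which change is set against which. The objective says *explore*, while the Discussion claims verification.

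With nothing fixed in advance, a near-zero arm difference at week 18, a fall in controls after supply, or a similar response in both arms could each be reported as confirmation. Each can occur with no insole effect. The week-52 results will appear in a paper whose title is to identify it as coming from a randomised controlled trial, so readers could take an uncontrolled result for randomised evidence of durability. The limitations discuss lack of blinding but not the loss of the untreated comparator.

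**Working it through.** **Plan's own figures.** No sample size or precision is stated for week 18 or week 52, so there is none to reproduce. From Sample size I take SD 2.22, effect 1.2 points, and 100 per group less 15% dropout: 100 × 0.85 = 85 per arm. The 70 per group given there belongs to the week-10 contrast and is not used. (The stated formula at 80% power gives 54, which is a separate matter.)

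**Assumptions.** Within-person correlation ρ = 0.7, 0.5 or 0.3 (not in the documents), equal variances and equal correlations between visits, and a normal approximation on the NRS scale.

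**Step 1: expected values.** I and C denote the intervention and control arms; negative means less pain.

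| Scenario | Week-10 difference, I − C | Week-18 difference, I − C | C change weeks 10-18 minus I change to week 10 | C change weeks 10-18 minus I change weeks 10-18 |
|---|---|---|---|---|
| Works equally in both arms (1.2), lasting, no drift | −1.2 | 0 | −1.2 − (−1.2) = 0 | −1.2 − 0 = −1.2 |
| No effect, no drift | 0 | 0 | 0 | 0 |
| No effect, drift of −0.5 in weeks 10-18 only (assumed) | 0 | 0 | −0.5 − 0 = −0.5 | −0.5 − (−0.5) = 0 |
| Benefit in I fades fully by week 18, C gains nothing | −1.2 | 0 | 0 − (−1.2) = +1.2 | 0 − 1.2 = −1.2 |

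The week-18 difference is 0 in every row. The non-concurrent comparison, which is the most literal reading of objective 2 and the Discussion, is 0 in both of the first two rows. The concurrent contrast separates those two rows and removes shared drift, but fading mimics benefit (last row). Algebraically it is the week-10 difference minus the week-18 difference.

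**Step 2: precision.** SD of change = 2.22 × √(2(1−ρ)). The SE is SD/√85 for one arm's change and SD × √(2/85) for a difference between two arms' changes.

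| ρ | SD of change | One-arm SE | Fall reaching p<0.05 (1.96 × SE) | Two-arm SE | 95% half-width | Half-width / 1.2 | Power of concurrent contrast at 1.2 |
|---|---|---|---|---|---|---|---|
| 0.7 | 1.72 | 0.187 | 0.37 | 0.264 | 0.52 | 43% | 99% |
| 0.5 | 2.22 | 0.241 | 0.47 | 0.341 | 0.67 | 56% | 94% |
| 0.3 | 2.63 | 0.285 | 0.56 | 0.403 | 0.79 | 66% | 85% |

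The half-widths apply to both the non-concurrent and the concurrent comparison. No margin for *similarly* is stated against which to read them.

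**Step 3: controls' own change.** With no insole effect, an assumed drift of 0.3 to 0.8 points over weeks 10-18 makes a before-after test in controls significant 18% (drift 0.3, ρ = 0.3) to 99% (drift 0.8, ρ = 0.7) of the time.

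**Step 4: calendar.** Recruitment ran from 16 September to 2 October 2023 (Trial status), a span of 16 days. With baseline 0 to 1 week after enrolment, week 10 falls between 25 November and 18 December 2023, and week 18 between 20 January and 12 February 2024. Controls therefore pass through weeks 10-18 almost together, in winter, while the intervention arm's change to week 10 is measured in autumn.

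**Step 5: dependence on the primary result.** The concurrent contrast correlates 1/√(2(1+ρ)) with the baseline-adjusted week-10 difference: 0.54, 0.58 and 0.62 for ρ = 0.7, 0.5 and 0.3.

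**Step 6: week 52.** Time since supply is about 52 − 2 = 50 weeks in the intervention arm and about 52 − 10 = 42 weeks in controls. Any arm difference compares longer with shorter availability, not insoles with no insoles.

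**The case against.** The strongest reply is that week 18 will not be read alone. The week-10 difference is randomised and focal, and the expected catch-up presupposes a gap at week 10. A gap of 1.2 that closes is not the same finding as no gap at either time. This stands: together, the two differences give the point estimate of the concurrent contrast. The plan does not name that combination, however, and closing of the gap can also mean fading in the intervention arm.

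Controls also give weekly pain scores up to week 10 without insoles, which show any drift before supply. This stands too, but those scores do not control for time, season or expectation during weeks 10-18.

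On weight, objective 2 only says *explore*, week 52 is labelled surveillance, and the missing blinding is already acknowledged. This limits the seriousness but does not justify the verification wording or the durability aim.

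A reader might infer more than the documents support:

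- *That no week-18 comparison exists.* One is named in Secondary objectives, Procedures and data collection, and the Discussion. What is missing is its specification.
- *That controls might be supplied as late as week 18, because Participant timeline labels the period weeks 10-18.* Procedures and data collection places supply at week 10, followed by eight weeks of observation.
- *That a seasonal trend of known size is at work.* No document gives one; the drifts above are assumed.

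**Conclusion.** The point holds as an overclaim in the Discussion and an unspecified analysis in the methods. The facts on supply are unambiguous, and the conclusion rests on design logic rather than on the assumed correlations.

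The literal week-18 comparison is non-concurrent and unblinded, has no margin, and has expectation 0 under both equal benefit and no effect. Its 95% half-width of about 0.5 to 0.8 points is 43% to 66% of the planned effect, so a non-significant gap is weak evidence of similarity. The week-18 arm difference becomes informative only beside the week-10 difference. Week 52 cannot show long-term effect or durability against no insoles.

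It would be wrong to infer that the trial's main result is compromised. The week-10 primary contrast, and the week-10 contrast among runners with baseline NRS of 3 or more, both precede supply to controls and are unaffected.

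**What to change.** 1. **Discussion.** Replace the verification claim with supportive or exploratory wording, and list the loss of the untreated comparator after week 10 as a limitation.
2. **Week 18.** Pre-specify the control arm's week 10-18 change minus the intervention arm's change over the same weeks. Label it supportive, and always show it with each arm's own change and the week-10 difference. State that it assumes the intervention arm has reached a plateau by week 10 (about 8 weeks of use, including a recommended three-week wearing-in), does not remove expectation, can be mimicked by fading, and is not independent of the primary result. If the non-concurrent comparison is kept for objective 2, report it as an estimate with its interval, not as a test of similarity.
3. **Week 52.** Report descriptively by arm, with time since supply (about 50 against about 42 weeks), and make no causal claim of long-term effect or durability against no insoles. Reword objective 3 and the post-market aim to match.

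The cost is wording in the objectives, the secondary-analysis section and the Discussion, plus one extra secondary contrast on week-10 and week-18 pain data already collected in both arms. Design, data collection and primary analysis do not change. The price is more modest long-term conclusions.

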Zoles ApS and affiliates have no role in the study, and are restricted from any involvement in the design of the study, execution, analyses, interpretation of data, writing of the manuscript, or in the decision to submit for publication. The Study Director has full authority of the trial administration and decision for publication.

Funding

This is an investigator-initiated trial. The funding for this study is provided by St Mary's University Faculty of Sport, Technology and Health Sciences (STHS) QR Funds. Zoles ApS has graciously contributed the customised 3D printed insoles for all study participants, valued at approximately £23,000. Zoles ApS is also responsible for supplying the 3D scanners

(DOMEscan/IBV, Instituto de Biomecanica de Valencia, 46022, Valencia, Spain) that are used to scan the participants' feet, training and support of St Mary's staff members.

Authors' contributions

FGL is the study director, he conceived the study, led the proposal and protocol development, primary supervisor overseeing the overall conduct of the study. SI is the principal investigator, leading the core investigative efforts. RM and CD shared the role of study chair; RM also acted as co-supervisor, while CD managed data collection. KT, also a study chair, contributed senior clinical trial expertise and senior supervision. All authors participated in designing the study, refining the protocol, and approved the final study registration and manuscript.

Acknowledgements

We express our thanks to the local parkrun organisers for their support and collaboration. Their assistance in participant recruitment will be crucial to this study's initiation and progress.

Figures

Figure 1: Zoles 3D-printed insole exemplar. Picture provided and used with permission from Zoles ApS.

Figure 2: Example of foot scanning process of a right foot using the DOMEscan/IBV 3D scanner.

Figure 3: Participant timeline in the SPIRIT (Standard protocol items: Recommendations for interventional trials) diagram

Figure 4: Visualisation of change in pain score in the intervention (blue) and control group (red), respectively (Example, not based on data).

Figure 1

[figure not shown]
Figure 2

Figure 3

| | STUDY PERIOD | | | | | | | | | | | Control group step allocation | Post-market surveillance | |
|---------------------------------------|--------------|------------|----------------------|---|---|---|---|---|---|---|---|-------------------------------|--------------------------|----|
| | Enrolment | Allocation | Primary Study Period | | | | | | | | | | | |
| TIMEPOINT (weeks) | -1 | 0 | 1 | 2 | 3 | 4 | 5 | 6 | 7 | 8 | 9 | 10 | 18 | 52 |
| ENROLMENT: | | | | | | | | | | | | | | |
| Eligibility screen | X | | | | | | | | | | | | | |
| Informed consent | X | | | | | | | | | | | | | |
| Foot scanning | X | | | | | | | | | | | | | |
| 3D printing of insoles | X | | | | | | | | | | | | | |
| Group allocation | | X | | | | | | | | | | | | |
| INTERVENTIONS: | | | | | | | | | | | | | | |
| Intervention (Zoles) | | | | | | | | | | | | | | |
| Control ("do-as-usual" until week 10) | | | | | | | | | | | | | | |
| ASSESSMENTS: | | | | | | | | | | | | | | |
| Baseline/end of study questionnaire | | X | | | | | | | | | | | | X |
| Outcome questionnaire | | | | | | | | | | | | | X | |
| 1. Running-related pain | | | X | X | X | X | X | X | X | X | X | X | X | |
| 2. GROC | | | X | X | X | X | X | X | X | X | X | X | X | |
| 3. Foot/footwear comfort | | | X | X | X | X | X | X | X | X | X | X | X | |
| 4. 5km completion time | | | X | X | X | X | X | X | X | X | X | X | X | |
| 5. Running-related injuries | | | X | X | X | X | X | X | X | X | X | X | X | |
| 6. Time-loss from running | | | X | X | X | X | X | X | X | X | X | X | X | |
| 7. Weekly milage | | | X | X | X | X | X | X | X | X | X | X | X | |
| 8. Weekly running exposure | | | X | X | X | X | X | X | X | X | X | X | X | |
| ADHERENCE: | | | | | | | | | | | | | | |
| Adherence to intervention | | | | | X | X | X | X | X | X | X | X | X | X |
| ADVERSE EVENTS: | | | | | | | | | | | | | | |
| Adverse events from using insoles | | | | | | | | | | | | | | |

Figure 4

Appendices

A

SPIRIT checklist

B

TIDieR intervention Checklist

C

Intervention leaflet 1

D

Intervention leaflet 2

E

Participant consent materials

F

Baseline questionnaire

G

Weekly follow-up questionnaire

H

WHO Trial Registration Data Set (Version 1.3.1)
